**Hospital Security Program for Engaging Communities with Firearm
Safe Storage Devices and Interventions: Data Collection Aim 2**

Study Protocol

January, 2024

Outline

1. Abstract
2. Overall objectives
3. Aims
 - 3.1 Primary outcome
 - 3.2 Secondary outcomes
4. Background
5. Study design
 - 5.1 Design
 - 5.2 Study duration
 - 5.3 Target population
 - 5.4 Accrual
 - 5.5 Key inclusion criteria
 - 5.6 Key exclusion criteria
6. Subject recruitment
7. Subject compensation
8. Study procedures
 - 8.1 Consent
 - 8.2 Procedures
9. Analysis plan
10. Human research protection
 - 10.1 Data confidentiality
 - 10.2 Subject confidentiality
 - 10.3 Subject privacy
 - 10.4 Data disclosure
 - 10.5 Data safety and monitoring
 - 10.6 Risk/benefit
 - 10.6.1 Potential study risks
 - 10.6.2 Potential study benefits
 - 10.6.3 Risk/benefit assessment

1. Abstract

To prevent workplace violence, in November 2021, Penn Medicine implemented the Evolv weapons detection system in Pennsylvania Hospital (1,2). For individuals who self-disclose they are carrying a weapon, or who are identified with weapon during screening, security guards offer the individual the option to leave with their weapon, or to place it in a safe, at the hospital, for storage. Security guards return the weapon when the patient or visitor is ready to leave. Beginning in July 2022 our team piloted a program in which security guards offer a cable lock and safety brochure when the gun owner returns to retrieve their firearm at the conclusion of their visit. To date, 47% of patients and visitors who stored their firearm with security have taken a cable lock when offered, resulting in over 300 firearm safety locks and brochures distributed to firearm owners. The Aims of this study are to: (1) Elucidate barriers and facilitators to implementing a hospital security screening firearm safety program through interviews with hospital security staff; (2) Design and pilot test a method for collecting data on storage device use among patients and visitors who accept firearm safety materials; (3) Conduct a pilot of distributing lockboxes and compare acceptance and usage rates to cable locks.

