3.2 Secondary outcome

The secondary outcome measures are from initial and follow-up survey responses: (1) firearm storage behavior, (2) likelihood of using cable lock within the next week (extremely unlikely to extremely likely scale).

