5.5 Key inclusion criteria

Individuals who are visitors or patients at Pennsylvania Hospital, are identified through the Evolv system as carrying a firearm, and who accept firearm safety materials OR any patient or visitor interested in receiving a firearm storage device who self-selects into the study by scanning the QR code on the study poster. For eligibility of the follow-up survey, participants must have responded yes to taking a cable lock

in the initial brochure survey or yes to receiving a firearm storage device shipped to their address from the poster survey.

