8.2 Procedures

Study procedure. A unique QR code linking directly to the survey will be embedded into our firearm safety brochure and study poster available in the entry hall of PAH. Participants who scan positive for a firearm and are offered safety materials (inclusive of the brochure) will be informed that survey participation is optional, but that it is helpful to our efforts, and that participation will be compensated with a \$10 Amazon gift card for completing the initial survey and a \$20 Amazon gift card for completing the follow-up survey. Individuals who decline the device will also be eligible for the initial survey via the poster QR code. Gift cards will be distributed digitally via text in accordance with the participants consent to share their phone number. Only eligible participants will receive a text with a link to complete the optional follow-up survey.

Participants who self-select into the study via the study poster will be linked to the initial survey in Qualtrics with one re-worded question based on context. Individuals will receive \$10 Amazon gift card for completing the initial survey and a \$20 Amazon gift card for completing the follow-up survey. Only eligible participants will receive a text with a link to complete the optional follow-up survey.

Initial Survey via Brochure. Upon scanning the QR code on the brochure, an individual will be brought directly to the initial Qualtrics survey. The first question of the survey is a statement outlining that the individual's participation is voluntary and informed. The individual must select agree or disagree before proceeding with the survey. If the individual chooses to agree, they will then begin the initial survey. After completion of the survey, they will receive a text message with their Amazon giftcard information within 1-2 weeks. The text will read, "Hello, this is Penn Medicine. Thank you for participating in our survey. As an appreciation for your time, please see below for your gift card information: [INSERT GIFT CARD #]"

This initial survey will focus on the following elements. Survey language may be refined during the research process:

- 1.
2. To receive an Amazon gift card and participate in future follow-up surveys, please enter your phone number.
3. Most recent visit to Penn Medicine (mm/dd/yyyy)
4. Did you get a cable lock today?
 - a. Yes
 - b. No
5. [IF NO #3] What's the reason you didn't accept one?
 - a. Already have one
 - i. [LOGIC] How often do you use it?

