 1. Every time I store my device
 2. Almost every time I store my device
 3. Almost never when I store my device
 - ii. [LOGIC] What's your preference for storing your firearm? [text field]
 - b. Prefer different storage device
 - i. [LOGIC] Which of the following storage devices would you prefer?
 1. Lock box
 2. Trigger lock
 3. Gun safe
 4. Calmshell / "life jacket"
 5. Gun cabinet
 6. In-vehicle lock
 7. Other/key/PIN/biometric (please specify):
 - c. Don't want one
 - d. Not offered or not available
6. [IF YES #3] If you have accepted a device today, how likely are you to use it in the next week?
 - a. Extremely likely
 - b. Somewhat likely
 - c. Neither likely nor unlikely
 - d. Somewhat unlikely
 - e. Extremely unlikely
7. How do you usually store your firearm?
 - a. In a locked safe or gun cabinet
 - b. With a trigger lock or cable lock
 - c. Unlocked (not secured with a lock, in a locked container, or not stored in a locked cabinet)
 - d. Other (please specify)

Initial Survey via Poster. Upon scanning the QR code on the poster next to the distribution area, an individual will be brought directly to the initial Qualtrics survey. The first question of the survey is a statement outlining that the individual's participation is voluntary and informed. The individual must select agree or disagree before proceeding with the survey. If the individual chooses to agree, they will

then begin the initial survey. After completion of the survey, they will receive a text message with their Amazon giftcard information within 1-2 weeks. The text will read, "Hello, this is Penn Medicine. Thank you for participating in our survey. As an appreciation for your time, please see below for your gift card information: [INSERT GIFT CARD #]"

This initial survey will focus on the following elements. Survey language may be refined during the research process:

1. To receive an Amazon gift card and participate in future follow-up surveys, please enter your phone number.
2. Most recent visit to Penn Medicine (mm/dd/yyyy)
3. Are you interested in receiving a firearm storage device shipped to your address?
4. [IF NO #3] What's the reason you don't want one?
 - a. Already have one
 - i. [LOGIC] How often do you use it?
 1. Every time I store my device
 2. Almost every time I store my device
 3. Almost never when I store my device
 - ii. [LOGIC] What's your preference for storing your firearm? [text field]
 - b. Prefer different storage device

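### Brochure items 4 and 6 ask about *today*, so a lock-taker who scans on a later day and answers literally is recorded as not accepting and loses the likelihood item and the follow-up

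*Protocol*

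**What the plan says.** The Abstract (section 1) describes the hand-over: "security guards offer a cable lock and safety brochure when the gun owner returns to retrieve their firearm at the conclusion of their visit". Sections 5.1 and 8.2 place the QR code for the initial survey in that brochure. No section requires the code to be scanned on the day of the visit.

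The brochure survey in section 8.2 then runs as follows:

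- Item 3 asks for the visit date: "Most recent visit to Penn Medicine (mm/dd/yyyy".
- Item 4 is the gate: "Did you get a cable lock today".
- After No, item 5 asks "What's the reason you didn't accept one". The options are already having one, preferring another device, not wanting one, and "Not offered or not available".
- After Yes, item 6 asks "If you have accepted a device today, how likely are you to use it in the next week", on a five-point scale.
- Item 7, on usual storage, has no skip condition.

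Section 3.2 makes item 6 a secondary outcome: "likelihood of using cable lock within the next week". Section 5.5 sets the next gate for the brochure route: "For eligibility of the follow-up survey, participants must have responded yes to taking a cable lock". The follow-up text in section 8.2 repeats that restriction.

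**The concern.** Item 3 shows that the form does not take the survey day to be the visit day, but items 4 and 6 do. For someone who took a lock at the visit and scans some days later, the literally accurate answer to item 4 is No, and every later branch then treats that person as not having accepted a lock.

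Aim 2 is to collect data on device use among people who accept the materials. Three results are exposed:

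- Secondary outcome 2 loses genuine accepters.
- The follow-up loses the same people, and with them their storage since the visit and whether they used the device.
- The reasons for non-acceptance gain people who did accept. Section 5.1 sends those who decline the device to the poster, so genuine non-accepters in the brochure survey may be few, and a handful of false ones could matter.

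The loss depends on time to response. If an iteration of the method changes how soon people respond, recorded acceptance and follow-up eligibility could move with it. The poster survey uses a different gate (interest in a shipped device) and does not have this problem.

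**Working it through.** The protocol gives no figure for this point, so there is none to reproduce. The check traces the skip logic, then writes the loss as a formula. The skip labels in section 8.2 refer to item 3 although the lock question is listed as item 4. I read them as pointing to the lock question; nothing here turns on that offset.

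**Path of a lock-taker**

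| Step | Scans on the visit day | Scans later, reads *today* literally |
|---|---|---|
| Item 4, lock taken | Yes | No |
| Item 5, reason for not accepting | skipped | asked |
| Item 6, likelihood of use | asked | skipped |
| Item 7, usual storage | asked | asked |
| Follow-up (section 5.5) | eligible | not eligible |
| Counted as a completed survey | yes | yes |

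At item 5 no option covers a lock taken on an earlier day. The only one that fits is already having one, which leads to a question on how often it is used. A lock from the program would then be recorded as one already owned.

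**Does anything else recover these people?**

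- The follow-up paragraph in section 8.2 opens by saying that completers who give contact details will be texted. Section 5.5, the procedure text and the later sentence of the same paragraph limit the follow-up to eligible participants, so this does not clearly bring them back.
- Comparing the visit date in item 3 with the Qualtrics completion time could flag late responses. Section 10.1 restricts use of the completion time to checks for imposter participants, and a flag would not supply the skipped item 6.

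**Size**

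Let L be the share of lock-taker brochure responses made after the visit day, and q the share of those who take *today* literally. The share of responding lock-takers lost from item 6 and the follow-up is L × q. Both are assumptions; the protocol gives neither.

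| L | q = 0% | q = 50% | q = 100% |
|---|---|---|---|
| 10% | 0% | 5% | 10% |
| 30% | 0% | 15% | 30% |
| 60% | 0% | 30% | 60% |

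The table shows only how the loss scales. It does not estimate the loss.

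**After rewording.** If items 4 and 6 refer to the visit, the accurate answer of a late-scanning lock-taker is Yes. The loss from this cause is then 0 for every L and q.

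**The case against.** The strongest reply is that few people may be affected. Item 3 comes immediately before item 4 and may lead respondents to read *today* as the day of the visit. Someone holding the lock who is then asked why they did not accept one has a cue that No was the wrong answer. Security mentions the survey around hand-over, so same-day scanning is plausible, and the imposter check in section 10.1 compares completions with daily lock distribution. Section 8.2 also says that survey language may be refined. All of this stands as a limit on size and weight. None of it corrects the wording: the literal answer is still the one that misroutes, and permission to refine the items only makes the change easy.

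A reader might infer more than the protocol supports:

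- *That every late-scanning lock-taker is lost.* Only those who read *today* literally are.
- *That the loss can be set against a monthly volume.* The Background gives 408 firearms in 5 months and 47% uptake, so 408 / 5 × 0.47 = 38.4 a month. But the 408 come from the first 5 months after November 2021, before locks were offered in July 2022. They count firearms, and the product is projected lock-takers, not survey respondents.
- *That follow-up item 2 is the only source on use.* Follow-up item 1 also records storage with a trigger or cable lock, and the branch for those who already have a lock asks how often it is used.
- *That new use of the lock contaminates the baseline storage answer.* Item 7 asks about usual storage, which denotes habit. The protocol does not show that a few days of use would change the answer.
- *That the response rate is biased.* A misrouted person still completes the survey.

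**Conclusion.** The concern holds as a wording and routing fault in brochure items 4 and 6. It can remove genuine lock-takers from secondary outcome 2 and from the follow-up, and place them among those giving reasons for not accepting.

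The conclusion rests on two readings: that the brochure leaves the hospital with the owner, which is inferred from hand-over at exit and not stated in those words, and that some people scan on a later day and answer literally. A scan later on the same day is unaffected.

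The size cannot be determined from the protocol and may be small. The primary outcome is untouched. The change is still worth making, because it costs almost nothing and an item 6 that was never asked cannot be recovered afterwards.

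**What to change.** - Item 4: 'At the visit when you received this brochure, did you take a cable lock?'
- Item 6: 'How likely are you to use the cable lock you took at that visit in the next week?' Keep the five-point scale. If wanted, add 'already using it' as a separate response option and report it apart from the scale. Putting it into the question itself would ask two things at once.
- Base follow-up eligibility in section 5.5 and in the follow-up text of section 8.2 on the reworded item 4.

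Anchoring the usual-storage item to the time before the visit is optional. If it is done, change brochure item 7 and poster item 6 together so that the two versions stay comparable.

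Reporting days from visit to response is not part of this fix. It would need the completion time, and section 10.1 would have to be changed first.

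The cost is two wording changes in Qualtrics, a matching line in the protocol and a minor IRB amendment, with no added burden for respondents.

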3.3 Exploratory outcomes

To compare survey response rates between several different variations of survey distribution: web survey accessed via QR code posted in the entry hall; web survey accessed via QR code included on the safety brochure; follow-up survey link administered by text message.

4. Background

Firearm injury is the leading cause of death of children in the U.S. and Philadelphia (3). Our work shows unintentional injuries are the leading cause of nonfatal firearm injuries with rates disproportionately higher in Black communities (Figure 1). As in Philadelphia, forty percent of American adults live in a household with at least one firearm, and two thirds of these have at least one firearm that is unlocked (4–6). Secure storage of firearms can prevent youth suicide, unintentional injury, intimate partner homicide, theft, and violent crime (7–10). Education and legislation have had limited impact on promoting safe firearm storage (11–15).

[figure not shown]

Figure 1: Annual U.S. Firearm Injury Rates per 100,000 by Intent, Age, Race, and Ethnicity, 2019-20 (Kaufman...Delgado, under review)

Penn Medicine prohibits firearms within its buildings. In November 2021, Penn Medicine implemented the Evolv weapons detection system in entrances to Pennsylvania Hospital and its medical office buildings (2). In the first 5 months of the program, there were over 300,000 screening encounters and 408 firearms identified and stored by hospital security. In July 2022 our team piloted an innovative program in which security guards offer a firearm cable lock and safety brochure when the gun owner return to retrieve their firearm at the conclusion of their visit. To date, 47% of patients and visitors who stored their firearm with security have taken a cable lock when offered, resulting in over 300 firearm safety locks and brochures distributed to firearm owners.

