5.1 Design

Aim 2 of this research study is to design and pilot test a method for collecting data on storage device use among patients and visitors who accept firearm safety materials or are interested in receiving a firearm storage device shipped to their address. The study design is an iterative pilot test of survey data collection methods and determination of scalability and feasibility for distribution of firearm storage devices. The study population and sample will be (a) individuals who are patients or visitors to PAH who are screened

for a firearm, screen positive, and accept a firearm safety brochure and storage device OR (b) individuals interested in receiving a firearm storage device and self-scan the unique QR code on the study poster in the entry hall of PAH with minimal or no security supervisor engagement. A unique QR code linking directly to the initial survey will be embedded into the firearm safety brochure as well as the poster in the entry hall of PAH next to the distribution area. Individual group (a) will be informed by security that survey participation is optional, but that it is helpful for our efforts, and that participation will be compensated with a \$10 Amazon gift card for the initial survey and a \$20 Amazon gift card for completing the follow-up survey. Individual group (b) will not be actively engaged by security, and will self-enroll in the study by viewing the posted signage and completing the QR code linked survey. Individuals who decline the device will also be eligible for the initial survey via the poster QR code, but they will not be eligible for the follow-up survey.

The primary outcome measure is survey response rate: whether an eligible visitor or patient completed the firearm storage survey after accepting firearm safety materials or after scanning the QR code on the poster. This will be measured through Qualtrics survey completion rate and PAH Evolv security system foot traffic. We will use the survey completion rate as the numerator and the number of people scanning positive for a firearm as the denominator for this rate.

The secondary outcome measures are from initial and follow-up survey responses: (1) firearm storage behavior, (2) likelihood of using cable lock within the next week (extremely unlikely to extremely likely scale). These outcomes are directly tied to questions asked in both surveys.

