 - i. [LOGIC] Which of the following storage devices would you prefer?
 1. Lock box
 2. Trigger lock
 3. Gun safe
 4. Calmshell / "life jacket"
 5. Gun cabinet
 6. In-vehicle lock
 7. Other/key/PIN/biometric (please specify):
 - c. Don't want to share my address
 - i. [LOGIC] Please select which of the following you'd be open to:
 1. Returning to Penn Medicine to pick up a free cable lock
 2. Receiving a free cable lock locally
 3. Other (please specify)
5. [IF YES #3] What is the best US shipping address for you?
 - a. [Text box fields for street, apt, city, zip, name]
6. How do you usually store your firearm?
 - a. In a locked safe or gun cabinet
 - b. With a trigger lock or cable lock
 - c. Unlocked (not secured with a lock, in a locked container, or not stored in a locked cabinet)
 - d. Other (please specify)
7. Once you receive your cable lock, how likely are you to use it in the next week?
 - a. Extremely likely

- b. Somewhat likely
- c. Neither likely nor unlikely
- d. Somewhat unlikely
- e. Extremely unlikely

Follow-up Survey: Participants who complete the initial survey and who agree to provide contact information will be contacted via text message 1 month after enrollment for a follow-up survey that adds questions about if and how participants have changed their storage behavior. The text language will read:

“Hello, this is Penn Medicine. Thank you for completing our initial survey. If you’re interested in taking the follow-up survey, please click the survey link below: [INSERT LINK]”

Participants will receive the second Amazon gift card incentive 1-2 weeks after completion of this survey. “Hello, this is Penn Medicine. Thank you for participating in our survey. As an appreciation for your time, please see below for your gift card information: [INSERT GIFT CARD #]”

The follow-up survey questions are subject to be amended based on the principal investigators’ discretion. Eligible participants from the initial survey, those who answered yes to accepting a cable lock, will be asked the following questions to understand if their behavior changed:

1. Since you’ve visited Penn Medicine, how have you stored your firearm? [option selection]
 - a. Participants select [a] in a locked safe or gun cabinet, b) with a trigger lock or cable lock, c) unlocked (not secured with a lock, in a locked container, or not stored in a locked cabinet), d) other (please specify) with an open comment box]

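### The storage question asks about usual storage in both initial surveys but drops the word at follow-up, so part of any before-after difference may come from the wording.

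*Protocol*

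**What the plan says.** Sections 3.2 and 5.1 of the protocol take storage behaviour, the first secondary outcome, from the initial and the follow-up surveys. Section 5.1 adds: "These outcomes are directly tied to questions asked in both surveys".

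The questions themselves are in Section 8.2:

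- Initial survey via brochure, item 7: "How do you usually store your firearm".
- Initial survey via poster: "6. How do you usually store your firearm", the same stem.
- Follow-up survey, item 1: the period begins when the person "visited Penn Medicine, how have you stored your firearm".

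Follow-up participants "will be contacted via text message 1 month after enrollment for a follow-up survey". Section 8.2 gives the purpose of that form: those eligible "will be asked the following questions to understand if their behavior changed".

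Section 9 lists the four storage categories for this outcome and names no before-after test. Section 8.2 allows survey language to be refined and leaves the follow-up questions open to amendment at the principal investigators' discretion.

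**The concern.** The four answer categories are the same at both times, which invites a direct comparison of the two distributions or of each person's two answers. That comparison needs the two questions to ask for the same thing. The initial stem asks for a habit. The follow-up stem sets a period and leaves open whether the habit in that period or any storage in it is wanted.

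At stake is the interpretation of the only outcome that records how firearms are stored before and after the programme. If answers differ, the study cannot say how much of the difference is behaviour and how much is the question. A separate analysis plan could not repair this, because the information is lost when the question is answered. The matter also reaches past this pilot: Aim 2 is to design a way of collecting data on device use, and Section 4 looks ahead to randomised trials of sustained safe storage, into which the item could be carried.

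**Working it through.** The protocol gives no sample size, power or expected change for this outcome, so there is no figure to reproduce. The check compares the items.

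| Feature | Initial, brochure (item 7) and poster (item 6) | Follow-up (item 1) |
|---|---|---|
| Frequency word | usually | none |
| Period | none stated | since the visit, about one month |
| Categories | locked safe or cabinet; trigger or cable lock; unlocked; other | the same four |
| Which firearm | not specified | not specified |
| One answer or several | not stated | not stated |

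Two rows differ. A before-after comparison needs a period at follow-up, so the period is not a fault in itself. The frequency word is what changes the thing being measured.

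Take two people whose habits do not change, and apply each reading of the follow-up item.

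1. **Usually unlocked, locked now and then during the month.** The initial answer is unlocked. At follow-up, the typical-storage reading gives unlocked again. The any-storage reading allows either unlocked or lock as a truthful answer.
2. **Usually locked, left unlocked now and then during the month.** The initial answer is lock. At follow-up, the typical-storage reading gives lock again. The any-storage reading allows either lock or unlocked.

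Two results follow. If everyone adopts the typical-storage reading, the wording contributes nothing. If some adopt the any-storage reading, the wording can move answers in both directions. The net effect depends on how many people of each kind there are and how they choose, and the protocol gives none of these quantities.

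Next, whether the other follow-up items close the gap:

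- Item 2 asks, yes or no, whether the supplied device has been used. One use and nightly use give the same answer, so it cannot show which reading lay behind item 1.
- Item 3 is a free-text question on other changes. It may pick up some real change but does not make the two storage items parallel.
- The initial forms do contain a graded-use question (every time, almost every time, almost never). It goes only to people who declined a device because they already have one, and under Section 5.5 they are not eligible for follow-up.

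**The case against.** The strongest reply is that the follow-up item, with its since-visit period, is naturally read as how the firearm has been kept over that time, which is close to usual storage. The word *any* does not appear in it. On that reading nothing is wrong. Further, Section 5.4 presents the study as an evaluation of data collection methods, the primary outcome is response rate, Section 9 plans no before-after test, items 2 and 3 ask about use and change directly, and the wording may be amended.

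Much of this stands. The defect is an ambiguity, not a known difference in what is measured, and it concerns a secondary outcome. It does not dispose of the point. Section 8.2 states that the follow-up is there to detect change, the respondent's reading is not recorded, and freedom to amend is not a commitment to match the stems.

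Three stronger readings are tempting and are not supported:

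- **That the shift favours the programme.** Only people who took or asked for a device are followed up, so occasional lock use is plausible. But the second case above moves answers the other way, and an occasional locker may still truthfully answer unlocked.
- **That the shift can be put in percentage points.** Section 4 says of households with a firearm that "two thirds of these have at least one firearm that is unlocked". That is a household figure. It is not the share of these participants who usually store unlocked, and nothing in the protocol gives the share who would change their answer through occasional use.
- **That the unspecified firearm is part of the wording change.** It is left open in the same way at both times. An owner of several firearms may answer about different ones, which adds noise but is not a difference between the stems. Tying the item to the firearm brought to the visit would also sit uneasily with the aim in the abstract of keeping scrutiny to a minimum.

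**Conclusion.** The point holds as a non-parallel question. The two storage items share their categories but not their stem, and the follow-up stem admits two readings, only one of which matches the initial question. Part of an apparent change between categories may therefore come from the wording. The contribution is zero if all respondents report typical storage. Otherwise its size and sign cannot be determined from the protocol. The conclusion rests on the item texts in Section 8.2 and on the stated purpose of detecting change. It does not assume that a formal test will be run or that the pilot will claim an improvement. This should be corrected because it is cheap and cannot be repaired once data are in. It does not threaten the primary outcome.

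**What to change.** Reword follow-up item 1 to: *Since you visited Penn Medicine, how have you usually stored your firearm?* Keep the four categories, and state in all three forms that one answer is to be chosen. Leave the initial stem as it is, so that initial answers already collected as a single choice remain usable.

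The change is one word in one item and a single-choice setting in three forms, which Section 8.2 already permits. The one drawback is that follow-up answers collected under the present wording should be reported separately for this outcome and not pooled with later ones. Items 2 and 3 can stay as supporting information.
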